7 STATISTICAL CONSIDERATIONS

The primary objective of this study is to determine if the use of unilateral adrenalectomy is associated with normalization and/or improvement of hypertension, diabetes, osteoporosis, hypercholesterolemia, and/or obesity compared to medical treatment-only arm.

Patients with subclinical hypercortisolism will be randomized to adrenalectomy or medical treatment as defined above and followed for 6 months. At the end of 6 months, the patients who were in the medical treatment-only arm will all be offered an adrenalectomy. Patients with subclinical hypercortisolism tend to have high prevalence of metabolic consequences, specifically hypertension, diabetes, obesity and/or osteoporosis.

To be conservative, the primary goal of this study will be to determine if the use of adrenalectomy is associated with 35% who have improvement vs. 5% who improve over 6 months without surgery as defined for any one or more of the following associated complications: hypertension, diabetes, osteoporosis, hypercholesterolemia, and/or obesity. With 31 patients per arm (62 total), there would be 80% power to detect a difference of this magnitude using a 0.05 significance level two-tailed Fisher's exact test.

For the potential 31 patients initially randomized to observation and then undergoing an adrenalectomy at 6 months, the level of MAP, systolic, and diastolic pressure at 6 months but just before surgery will be compared to these values in the potential 31 patients initially randomized to immediate adrenalectomy 6 months after surgery using a Wilcoxon rank sum test. In addition, in the patients initially randomized to observation the changes in MAP from baseline to 6 months of observation as well as the declines in systolic and diastolic pressure from 6 months of observation until 6 months after surgery will be compared with a Wilcoxon signed rank test. Other important continuous parameters such as change in weight, triglycerides, total, HDL and LDL cholesterol, A1c, fasting glucose, and bone density may also be compared within patients using Wilcoxon signed rank test.

Abbreviated Title: Subclinical Hypercortisolism

Version Date: 12/19/2016

It is expected that 15-20 eligible patients may be able to enroll on this trial per year. In order to enroll 62 evaluable patients, it is anticipated that 3-4 years would be required. In order to allow for a small number of inevaluable patients, the accrual ceiling will be set at 66 patients.

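### The within-patient blood-pressure analysis names MAP only before surgery and systolic/diastolic pressure only across it, so no measure has a like-for-like control interval

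*Combined protocol and SAP*

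**What the plan says.** Section 7 plans two blood-pressure analyses beyond the primary composite.

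- **Between randomized arms.** For the observation arm, "the level of MAP, systolic, and diastolic pressure at 6 months but just before surgery will be compared to these values" in the patients "initially randomized to immediate adrenalectomy 6 months after surgery using a Wilcoxon rank sum test". All three measures are named.
- **Within the delayed-surgery arm.** The next sentence names "the changes in MAP from baseline to 6 months of observation as well as the declines in systolic and diastolic pressure" and continues: "from 6 months of observation until 6 months after surgery will be compared with a Wilcoxon signed rank test". MAP belongs to the first interval only, and systolic and diastolic pressure to the second only. No significance level, sidedness or contrast between intervals is given.

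The sentence after that makes other within-patient comparisons optional. It ends: "A1c, fasting glucose, and bone density may also be compared within patients using Wilcoxon signed rank test". Its list contains no blood pressure and gives no interval, so it does not fill the gap.

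**The concern.** A patient who is observed for 6 months and then operated on can serve as his or her own control, provided the same quantity is measured over both periods. The sentence in Section 7 does not provide for that, and it can be read in two ways.

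- **Reading A: the two changes are compared with each other.** A MAP change is then set against a systolic or diastolic change. These are different quantities, so identical behaviour in the two periods gives a non-zero expected difference.
- **Reading B: each change is tested against zero.** Systolic and diastolic pressure are then tested only across surgery, and MAP only before it. No measure is seen in both periods.

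Ordinary change cannot be ruled out. Section 3.1 commits to guideline-based management of the metabolic conditions, and Section 8.5 says observed patients receive standard medical treatment. If pressure falls for that reason, this analysis could be taken to credit surgery with it. The sentence also leaves the choice of measures and contrast open until the data are seen.

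**Working it through.** **The plan's own figure.** Section 7 gives one power statement: 80% for the primary two-sided Fisher test with 31 per arm, 35% vs 5%. Full enumeration gives 80.9%, so it reproduces. No power, SD or expected change is given for blood pressure, and the present point does not rest on the primary figure.

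**Parameters side by side (Section 7).**

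| Analysis | MAP | Systolic | Diastolic |
|---|---|---|---|
| Between arms at 6 months | yes | yes | yes |
| Within patient, baseline to 6 months of observation | yes | no | no |
| Within patient, 6 months of observation to 6 months after surgery | no | yes | yes |

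The last two rows share no column.

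**Assumptions for the arithmetic.** n = 31; MAP = (SBP + 2 × DBP)/3; no surgical effect; the same fall of 10/4 mmHg in each interval; visit SDs for SBP/DBP of 8/5 or 12/8 mmHg; SBP–DBP correlation 0.6; visit errors independent over time. Only n comes from the documents.

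**Reading A.** The MAP change is −(10 + 2 × 4)/3 = −6 mmHg.

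- Systolic minus MAP change: −10 − (−6) = −4 mmHg, which appears to favour surgery.
- Diastolic minus MAP change: −4 − (−6) = +2 mmHg, which appears to count against it.

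The variance of the systolic contrast is 2Var(S) + 2Var(M) + 2Cov(S,M).

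- SDs 8/5: Var(M) = (64 + 100 + 96)/9 = 28.9 and Cov(S,M) = (64 + 48)/3 = 37.3. The variance is 128 + 57.8 + 74.7 = 260.4, SD 16.1. Then 4√31/16.1 = 1.38, a normal-approximation rejection rate of about 28%.
- SDs 12/8: Var(M) = (144 + 256 + 230.4)/9 = 70.0 and Cov(S,M) = (144 + 115.2)/3 = 86.4. The variance is 288 + 140.1 + 172.8 = 600.9, SD 24.5. Then 4√31/24.5 = 0.91, about 15%.

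Simulation of the signed rank test (4,000 trials per setting) gives about 25% and 15%; repeat runs agree within about two points. At a drift of 3/1.5 mmHg the rate is 5–7%, and at zero drift about 5%. The diastolic contrast at 10/4 mmHg rejects in about 13% and 8–9%, almost always against surgery (in its favour in 0.2% and 0.8%).

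**Reading B, with drift in SDs of a 6-month change (assumed range, no surgical effect).**

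| Drift | Surgical interval tested alone | Same-measure contrast |
|---|---|---|
| 0 | 4.6% | 4.9% |
| 0.2 | 18% | 4.7% |
| 0.35 | 45% | 4.9% |
| 0.5 | 75% | 4.6% |

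The middle column is a property of any uncontrolled before-after test. It would be the same if all three measures were tested against zero in both intervals. It therefore shows what the missing contrast costs, not what the MAP/systolic mismatch costs.

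**Price of the contrast.** With visit SD σ, a single change has SD σ√2. The difference of two adjacent changes, y₂ − 2y₁ + y₀, has SD σ√6, larger by √3 = 1.73. For a true 10 mmHg systolic effect and no drift, simulated power is about 99% (σ = 8) or 87% (σ = 12) for the before-after test, and 77% or 42% for the contrast.

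**The case against.** The strongest reply is that the trial does not need this sentence to separate surgery from ordinary change. The rank sum comparison immediately before it sets operated against observed patients, by randomization, for all three measures. That stands. A reader might infer from the mismatch that the trial as a whole cannot distinguish a surgical effect on blood pressure from drug-driven change; the documents do not support this.

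A reader might also infer that a steady fall will be reported as an effect of surgery. Section 7 does not say how the within-patient result will be interpreted. Under Reading A most simulated trials show no difference even at the 10/4 mmHg drift, and the diastolic contrast errs the other way. Under Reading B the MAP test in the observation period is itself a drift check: in that scenario it is significant in about 98% or 76% of trials, so a fall before surgery would usually be visible.

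The drift assumption is also open to challenge. A fall of 10/4 mmHg in each interval means 20/8 mmHg over a year without any surgical effect. Section 1.2 cites one unoperated group with no improvement in blood pressure and another with 0% improved and 50% worsened. Section 7 assumes only 5% improve on any component without surgery. If pressure drifts upward, false declines nearly vanish.

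Finally, this may be a drafting slip, with all three measures meant for both intervals. That is plausible, but it is the only prespecified within-patient blood-pressure analysis and the text still has to say what will be done.

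**Conclusion.** The point holds for the secondary within-patient blood-pressure analysis of the delayed-surgery arm, and only there. As written, no measure is analysed in both intervals, so the observation period cannot act as a like-for-like control. This follows from the text alone and needs no assumption.

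Its numerical size does need assumptions, because the documents give neither a blood-pressure SD nor an expected change. The mismatch itself accounts for a systolic rejection rate of about 25% or 15% at a large assumed drift, 5–7% at a modest one, and no excess at zero drift. The much higher rates seen when the surgical interval is tested alone under large drift belong to before-after testing in general and should not be charged to the mismatch. The randomized rank sum comparison, the primary Fisher test and the sample size are untouched. The sentence should be corrected, but it does not threaten the trial's main conclusion.

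**What to change.** Rewrite the within-patient sentence in Section 7 along these lines:

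*For each of MAP, systolic and diastolic pressure in the delayed-surgery arm, the change from baseline to 6 months of observation and the change from 6 months of observation to 6 months after surgery will each be tested by a two-sided Wilcoxon signed rank test. In addition, the within-patient difference between the two changes will be tested by a two-sided Wilcoxon signed rank test. Attribution to surgery will rest on this contrast and on the randomized comparison, not on the before-after test alone.*

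The contrast should be added and the before-after tests kept, because of the power loss shown above.

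Use the same form for other continuous measures only where they are scheduled at M0, M6 and M12. Bone density does not qualify: the calendar in Section 3.3.2 gives the non-operative arm DEXA at baseline and then from M18.

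The cost is a short text change, with no added patients or visits. Section 5.4 re-evaluates the non-operative arm every 3 months from M0 to M18, which covers the three time points. Because the Section 3.3.2 calendar has no vital-signs row, the text should also confirm that blood pressure is recorded at those visits.

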8 HUMAN SUBJECTS PROTECTIONS

8.1 RATIONALE FOR SUBJECT SELECTION

Subjects from both gender groups and all racial/ethnic groups are eligible for this study if they meet the eligibility criteria. Efforts will be made to extend accrual to a representative population.

8.2 PARTICIPATION OF CHILDREN

Because adrenal neoplasms are exceedingly rare in children and when present are more likely to be malignant, children will not be enrolled in this study.

8.3 PARTICIPATION OF SUBJECTS UNABLE TO GIVE CONSENT

Adults unable to give consent are excluded from enrolling in the protocol. However re-consent may be necessary and there is a possibility, though unlikely, that subjects could become decisionally impaired. For this reason and because there is a prospect of direct benefit from research participation (section 8.4), all subjects will be offered the opportunity to fill in their wishes for research and care, and assign a substitute decision maker on the “NIH Advance Directive for Health Care and Medical Research Participation” form so that another person can make decisions about their medical care in the event that they become incapacitated or cognitively impaired during the course of the study. Note: The PI or AI will contact the NIH Ability to Consent Assessment Team for evaluation. For those subjects that become incapacitated and do not have pre-determined substitute decision maker, the procedures described in MEC Policy 87-4 for appointing a surrogate decision maker for adult subjects who are (a) decisionally impaired, and (b) who do not have a legal guardian or durable power of attorney, will be followed.

8.4 EVALUATION OF BENEFITS AND RISKS/DISCOMFORTS

Patients may experience personal benefit from the study if we find that adrenalectomy reverses the metabolic complications associated with subclinical hypercortisolism. Furthermore, there is the potential benefit of improving our ability to diagnose and predict the outcome of patients with subclinical hypercortisolism. Each individual patient would have a complication risk of <1% associated with the adrenalectomy.

Patients in the surgery group may experience personal benefit even during the follow-up period because they will be monitored for metabolic complications which may not have resolved with surgery. In these cases, we may find that the adrenalectomy did not reverse the complications and further treatment may be needed.

8.5 RISKS/BENEFITS ANALYSIS

The main risk of participation is related to the risk of complications in the adrenalectomy arm and worsening of the metabolic complications in patient in the observation arm. The risk of

Abbreviated Title: Subclinical Hypercortisolism

Version Date: 12/19/2016

adrenalectomy is less than 1% which would outweigh the potential benefit of reversal of metabolic complications. In patients in the observation arm, there may be worsening of the metabolic complications but all patients will cross over to the adrenalectomy arm after 6 months of follow up and will be medically treated as standard of care for the metabolic complications.

8.5.1 Risk of Radiation

This research study involves exposure to radiation from 1 PET/CT Scans (maximum 10 mCi per injection), 7 DEXA scans and 4 X-rays. This radiation exposure is not required for medical care and is for research purposes only. The amount of radiation received in this study is 2.7 rem which is below the guideline of 5 rem per year allowed for research subjects by the NIH Radiation Safety Committee. The average person in the United States receives a radiation exposure of 0.3 rem per year from natural sources, such as the sun, outer space, and the earth's air and soil. More information about radiation is available in the pamphlet, An Introduction to Radiation for NIH Research Subjects.

8.6 CONSENT AND ASSENT PROCESS AND DOCUMENTATION

All patients who are being considered for this trial will undergo informed consent prior to being enrolled on the trial. The PI or associate investigator will perform the consenting process. Patients and family members when applicable will be asked to read the consent and will be encouraged to ask questions. It will be stated clearly that participation in the research study is voluntary and that participants can withdraw from the study without losing benefits they would otherwise be entitled to. Patients will be enrolled after the consent document has been signed. Separate consents will be obtained for any surgical procedures performed.

8.6.1 Telephone consent

The informed consent document will be sent to the subject. An explanation of the study will be provided over the telephone after the subject has had the opportunity to read the consent form. The subject will sign and date the informed consent. A witness to the subject signature will sign and date the consent.

The original informed consent document will be mailed, via the US Postal Service or FedEx, back to the consenting investigator who will sign and date the consent form with the date the consent was obtained via telephone.

A fully executed copy will be returned via mail for the subject's records.

The informed consent process will be documented on a progress note by the consenting investigator and a copy of the informed consent document and note will be kept in the subject's research record.

8.6.2 Informed consent of non-English speaking subjects

We anticipate the enrollment of Spanish speaking research participants into our study. The IRB approved full consent document will be translated into that language in accordance with the Clinical MAS Policy M77-2.

If there is an unexpected enrollment of a research participant for whom there is no translated extant IRB approved consent document, the principal investigator and/or those authorized to

Abbreviated Title: Subclinical Hypercortisolism
Version Date: 12/19/2016

obtain informed consent will use the Short Form Oral Consent Process as described in MAS Policy M77-2, OSHRP SOP 12, 45 CFR 46.117 (b) (2), (If a study with an IND or IDE, also cite 21 CFR 50.27 (b) (2)). The summary that will be used is the English version of the extant IRB approved consent document. Signed copies of both the English version of the consent and the translated short form will be given to the subject or their legally authorized representative and the signed original will be filed in the medical record.

Unless the PI is fluent in the prospective subject's language, an interpreter will be present to facilitate the conversation. Preferably someone who is independent of the subject (i.e., not a family member) will assist in presenting information and obtaining consent. Whenever possible, interpreters will be provided copies of the relevant consent documents well before the consent conversation with the subject (24 to 48 hours if possible).

We request prospective IRB approval of the use of the short form process and will notify the IRB at the time of continuing review of the frequency of the use of the Short Form.

I am more irritable, I have sudden mood swings and angry outbursts

Always Often Sometimes Rarely Never

I have less self-confidence, I feel more insecure

Always Often Sometimes Rarely Never

I’m worried about the changes in my physical appearance due to my illness

Always Often Sometimes Rarely Never

I feel less like going out or seeing relatives or friends

Always Often Sometimes Rarely Never

I have had to give up my social or leisure activities due to my illness

Confidential

*Abbreviated Title: Subclinical Hypercortisolism**Version Date: 12/19/2016*

Always Often Sometimes Rarely Never

My illness affects my everyday activities such as working or studying

Always Often Sometimes Rarely Never

It's difficult for me to remember things

Always Often Sometimes Rarely Never

[figure not shown]
I'm worried about my health in the future

Always Often Sometimes Rarely Never

[figure not shown]
Abbreviated Title: Subclinical Hypercortisolism

Version Date: 12/19/2016

10.2 APPENDIX B – FDG PET/CT

FDG PET/CT scan results of patients with nonfunctioning adrenal masses versus patients with cortisol secreting adrenal masses.

Receiver operator characteristic (ROC) of FDG PET/CT scan results (AUC = 0.8506, p=0.01451).

Confidential

Abbreviated Title: Subclinical Hypercortisolism

Version Date: 12/19/2016

10.3 APPENDIX C GENERIC SF-36 QUALITY OF LIFE QUESTIONNAIRE

Generic SF-36 Quality of Life Questionnaire (26)

SF36 Health Survey

INSTRUCTIONS: This set of questions asks for your views about your health. This information will help keep track of how you feel and how well you are able to do your usual activities. Answer every question by marking the answer as indicated. If you are unsure about how to answer a question please give the best answer you can.			
1.	In general, would you say your health is: (Please tick one box.)		
	Excellent		
	Very Good		
	Good		
	Fair		
	Poor		
2.	Compared to one year ago , how would you rate your health in general now ? (Please tick one box.)		
	Much better than one year ago		
	Somewhat better now than one year ago		
	About the same as one year ago		
	Somewhat worse now than one year ago		
	Much worse now than one year ago		
3.	The following questions are about activities you might do during a typical day. Does your health now limit you in these activities? If so, how much? (Please circle one number on each line.)		
	Activities	Yes, Limited A Lot	Yes, Limited A Little
		1	2
		3	Not Limited At All
3(a)	Vigorous activities, such as running, lifting heavy objects, participating in strenuous sports	1	2
3(b)	Moderate activities, such as moving a table, pushing a vacuum cleaner, bowling, or playing golf	1	2
3(c)	Lifting or carrying groceries	1	2
3(d)	Climbing several flights of stairs	1	2
3(e)	Climbing one flight of stairs	1	2
3(f)	Bending, kneeling, or stooping	1	2
3(g)	Waling more than a mile	1	2
3(h)	Walking several blocks	1	2
3(i)	Walking one block	1	2
3(j)	Bathing or dressing yourself	1	2
4.	During the past 4 weeks , have you had any of the following problems with your work or other regular daily activities as a result of your physical health ? (Please circle one number on each line.)		
		Yes	No
4(a)	Cut down on the amount of time you spent on work or other activities	1	2
4(b)	Accomplished less than you would like	1	2
4(c)	Were limited in the kind of work or other activities	1	2
4(d)	Had difficulty performing the work or other activities (for example, it took extra effort)	1	2
5.	During the past 4 weeks , have you had any of the following problems with your work or other regular daily activities as a result of any emotional problems (e.g. feeling depressed or anxious)? (Please circle one number on each line.)		
		Yes	No
5(a)	Cut down on the amount of time you spent on work or other activities	1	2
5(b)	Accomplished less than you would like	1	2
5(c)	Didn't do work or other activities as carefully as usual	1	2

*Abbreviated Title: Subclinical Hypercortisolism**Version Date: 12/19/2016*

6. During the past 4 weeks , to what extent has your physical health or emotional problems interfered with your normal social activities with family, friends, neighbours, or groups? (Please tick one box.)							
Not at all 							
Slightly 							
Moderately 							
Quite a bit 							
Extremely 							
7. How much physical pain have you had during the past 4 weeks ? (Please tick one box.)							
None 							
Very mild 							
Mild 							
Moderate 							
Severe 							
Very Severe 							
8. During the past 4 weeks , how much did pain interfere with your normal work (including both work outside the home and housework)? (Please tick one box.)							
Not at all 							
A little bit 							
Moderately 							
Quite a bit 							
Extremely 							
9. These questions are about how you feel and how things have been with you during the past 4 weeks . Please give the one answer that is closest to the way you have been feeling for each item.							
(Please circle one number on each line.)							
		All of the Time	Most of the Time	A Good Bit of the Time	Some of the Time	A Little of the Time	None of the Time
9(a)	Did you feel full of life?	1	2	3	4	5	6
9(b)	Have you been a very nervous person?	1	2	3	4	5	6
9(c)	Have you felt so down in the dumps that nothing could cheer you up?	1	2	3	4	5	6
9(d)	Have you felt calm and peaceful?	1	2	3	4	5	6
9(e)	Did you have a lot of energy?	1	2	3	4	5	6
9(f)	Have you felt downhearted and blue?	1	2	3	4	5	6
9(g)	Did you feel worn out?	1	2	3	4	5	6
9(h)	Have you been a happy person?	1	2	3	4	5	6
9(i)	Did you feel tired?	1	2	3	4	5	6
10. During the past 4 weeks , how much of the time has your physical health or emotional problems interfered with your social activities (like visiting with friends, relatives etc.) (Please tick one box.)							
All of the time 							
Most of the time 							
Some of the time 							
A little of the time 							
None of the time 							
11. How TRUE or FALSE is each of the following statements for you?							
(Please circle one number on each line.)							
		Definitely True	Mostly True	Don't Know	Mostly False	Definitely False	
11(a)	I seem to get sick a little easier than other people	1	2	3	4	5	
11(b)	I am as healthy as anybody I know	1	2	3	4	5	
11(c)	I expect my health to get worse	1	2	3	4	5	
11(d)	My health is excellent	1	2	3	4	5	

Thank You!

